4.17.2. Adverse Events

A patient's safety reporting period will commence on the date of randomization to the time of last participation in the study (Section 4.12).

An AE is defined as any untoward medical occurrence in a patient or clinical investigation subject administered a pharmaceutical product and that does not necessarily have a causal relationship with this treatment. An AE can therefore be any unfavorable and unintended sign (including an abnormal laboratory finding), symptom, or disease temporally associated with the use of a medicinal (investigational) product, whether or not related to the medicinal (investigational) product.

Adverse events will be classified according to the Medical Dictionary for Regulatory Activities (MedDRA™). Analysis of AEs will focus primarily on those events that first occur or worsen (increase in frequency or severity) after the first injection of study drug following randomization, (that is, TEAEs); however, all conditions/events reported on the PRE-EXISTING CONDITIONS AND ADVERSE EVENTS page of the case report form (CRF) will be retained in the study database and will be reported in the listings. Study drug overdose will also be reported as a TEAE. Study drug overdose is defined as documented evidence of study drug injection more than once in a 3-day period. Analyses of TEAEs will be based on all randomized patients.

The identification of TEAEs will be performed according to the following process. Each condition/event will be coded to a preferred term (PT). For each patient, events will be divided into 2 groups: baseline events will include all events present prior to the date of randomization and before the first injection of study drug post randomization, and post-baseline events will include all events present on or after the date of randomization and the date of first injection of study drug. The maximum severity level (mild, moderate, or severe) reported prior to randomization and the first injection of study drug among all baseline adverse events that code to the same lower level term will be reported. If severity is missing for a particular baseline adverse event, then "mild" will be assumed. For each post-baseline event, the maximum severity reported after randomization and the first injection of study drug will be compared with the maximum baseline severity for the corresponding lower level term. If severity is missing for a particular postbaseline adverse event, then "severe" will be assumed. When the maximum post-baseline severity exceeds the maximum baseline severity, the event will be classified as a TEAE.

The primary hierarchy (PT through System Organ Class [SOC]) associated with the lower level term will be assigned. The number of patients experiencing a TEAE will be compared between treatments at the PT and SOC levels.

A by-patient listing of all adverse events, treatment-emergent or not, will be provided.

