#### **12.2.9.1. Adverse Events**

An AE is any untoward medical event associated with the use of a drug in humans, whether or not it is considered related to a drug. Adverse events will be coded from the actual term described by the investigator using the Medical Dictionary for Regulatory Activities (MedDRA) dictionary. Unless otherwise specified, AEs will be reported using the MedDRA system organ class and preferred term. Selected AEs may be reported using MedDRA high level terms.

All AEs will be listed by patient and may include information on treatment group, visit, preferred term, severity, seriousness, and relationship to the study medication, procedure, or device.

Treatment-emergent adverse events (TEAEs) will be defined as events that first occur or worsen (increase in severity) after the first injection of study drug following randomization. Study drug overdose will also be reported as a TEAE. Study drug overdose is defined as documented evidence of study drug injection more than once in a 3-day period. The count and proportion of patients with TEAEs will be summarized for each treatment group. Overall treatment group differences will be compared using Chi-square tests or Fisher's exact tests.

SAEs will also be summarized. The counts and proportion of patients experiencing the event of interest will be reported for each treatment arm. Treatment groups will be compared by Chi-square tests or Fisher's exact tests.

Permanent discontinuations of study drug due to AEs will be listed. The count and proportion of discontinuations will be reported. Time to discontinuation (due to AE) will be compared between treatment groups using a Cox proportional hazard regression model with treatment as a fixed effect. Kaplan-Meier curves for both treatment groups will be reported.

The number and percentage of patients who temporarily discontinue study drug will be compared between treatment groups with separate analyses for the reasons for the

discontinuation, such as AE. In addition, the number of patients with temporary discontinuations in categories of 1, 2, and  $\geq 3$  will be summarized by treatment groups.

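### The SAP's treatment-emergent algorithm turns an unchanged, ongoing condition with no post-baseline severity grade into a treatment-emergent event

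*SAP*

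**What the plan says.** SAP section 4.17.2 defines the events of interest as "those events that first occur or worsen (increase in frequency or severity) after the first injection of study drug following randomization". Protocol section 12.2.9.1 defines them as "events that first occur or worsen (increase in severity) after the first injection of study drug following randomization". Both require a new event or a worsening.

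The same SAP section then gives the operating rule, which it applies to every coded condition or event:

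- Baseline group: "baseline events will include all events present prior to the date of randomization and before the first injection of study drug post randomization".
- Post-baseline group: "post-baseline events will include all events present on or after the date of randomization and the date of first injection of study drug".
- Baseline reference: the highest grade "among all baseline adverse events that code to the same lower level term will be reported".
- Missing grade at baseline: "If severity is missing for a particular baseline adverse event, then 'mild' will be assumed".
- Missing grade after baseline: "If severity is missing for a particular postbaseline adverse event, then 'severe' will be assumed".
- Decision: "When the maximum post-baseline severity exceeds the maximum baseline severity, the event will be classified as a TEAE".

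The section also says that pre-existing conditions and adverse events share one case report form page. The number of patients with a TEAE is compared between arms by preferred term and by system organ class.

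**The concern.** Both groups are defined by whether an event was present, so one continuing condition belongs to both. Nothing in the SAP removes it from the second group. The two defaults for a missing grade then run in opposite directions, and the rule reads the gap between them as a worsening that nobody reported.

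Assuming the worst grade is a sensible caution for an event that starts after the first injection. Applied to one continuing record, it creates events instead. The rule ignores treatment, so these events appear at about the same rate in both arms. That is not cautious for a safety comparison: an equal background count in each arm lowers the relative risk and makes a real excess on dulaglutide harder to see in the preferred-term and organ-class tables.

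**Working it through.** **Step 1: the rule applied to a condition present in both periods.** Score mild = 1, moderate = 2, severe = 3. A missing baseline grade scores 1 and a missing post-baseline grade scores 3. Declare a TEAE if the later score exceeds the earlier one.

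| Baseline grade | Post-baseline grade | Scores | TEAE? |
|---|---|---|---|
| missing | missing | 1 vs 3 | yes |
| mild | missing | 1 vs 3 | yes |
| moderate | missing | 2 vs 3 | yes |
| severe | missing | 3 vs 3 | no |
| same recorded grade in both periods | | equal | no |

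The first three rows are the defect. The last row shows that the rule works when grades are recorded. The baseline reference is a maximum over records with the same lower level term, so a second baseline record graded severe blocks the false TEAE (3 vs 3). One graded mild or moderate does not. The cut-off combines randomization and first injection, which makes no difference to a condition that spans both.

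**Step 2: comparison with the definition.** In those three rows nothing need have started or worsened, so the result fails both the SAP definition and the Protocol definition.

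**Step 3: size, by illustration.** The plan has no figure to reproduce. About 4800 patients per arm follows from 9600 randomized 1:1. The missing share q, the proportion of patients v in whom the condition is ongoing across the first injection, and the true TEAE rates are assumptions.

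- False TEAE rate in each arm: f = v × q.
- Observed rate: p' = p + f(1 − p).
- The absolute difference becomes (p1 − p2)(1 − f), so it hardly moves. The relative risk and the power do.
- Power = Φ[(d − 1.96 × se0)/se1], where d is the observed difference, se0 uses the pooled rate and se1 the separate rates (two-sided 0.05).

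Take true rates of 3.0% vs 2.0% (144 vs 96 patients) and q = 2%.

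| v | f | Observed rates | RR | Power |
|---|---|---|---|---|
| none | 0 | 3.00% vs 2.00% | 1.50 | 88% |
| 5% | 0.0010 | 3.10% vs 2.10% | 1.48 | 87% |
| 10% | 0.0020 | 3.19% vs 2.20% | 1.45 | 86% |
| 30% | 0.0060 | 3.58% vs 2.59% | 1.38 | 80% |
| 90% | 0.0180 | 4.75% vs 3.76% | 1.26 | 66% |

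Worked example for the last row: 0.030 + 0.018 × 0.970 = 0.04746 and 0.020 + 0.018 × 0.980 = 0.03764, giving d = 0.00982, se0 = 0.00412 and se1 = 0.00412. Then (0.00982 − 1.96 × 0.00412)/0.00412 = 0.42, and Φ(0.42) = 0.66.

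With q = 1%, the 90% row gives RR 1.34 and power 77%.

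**The case against.** The strongest defence is that the mechanism depends on a case report form the documents do not show. Protocol 10.2.1 has sites record pre-existing conditions and, after consent, any change in them. On that reading an unchanged condition produces no later report, and a later report without a grade signals a change, for which a severe default is cautious. Protocol section 11 also provides for data review and computer edits, which might catch blanks. This stands as a limit on how often the problem occurs. It does not alter the analysis rule, which works from presence and says nothing about continuing records. The SAP itself expects missing grades in both periods.

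Several stronger readings are tempting, and the documents do not support them:

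- *Every ungraded ongoing condition becomes a TEAE.* A severe baseline record with the same lower level term prevents it.
- *Counts of severe TEAEs are inflated.* No table of TEAEs by severity is planned. The comparisons are of patients with any TEAE, by preferred term and organ class.
- *Hypertension and similar conditions are certain to be affected.* The documents do not say where hypertension is recorded; SAP 4.10 handles a limited set of historical illnesses through medical history questions.
- *A large share of patients is affected.* With 5 to 10 ongoing conditions each and 5% missing independently, 1 − 0.95^5 = 23% to 1 − 0.95^10 = 40% would have a false TEAE. Neither input is in the documents, and clustering of blanks within patients would lower the result.
- *The main safety conclusions are at risk.* SAP 4.17.1.2 uses adjudicated, investigator-reported or SAE data for most prespecified measures. Severe hypoglycemia and SAEs have their own analyses, and the listing of all adverse events keeps misclassified records visible.

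The SAP definition also mentions an increase in frequency, which neither the algorithm nor the Protocol uses. That is a separate wording mismatch, and removing it would change no result.

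**Conclusion.** The point holds on the text. An ongoing, unchanged condition with no post-baseline grade is classified as a TEAE unless its baseline reference grade is severe, against the SAP's and the Protocol's own definitions. It arises only where severity is missing. The false counts are about equal between arms, so they favour neither arm directly but pull relative risks in the TEAE tables toward 1.

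The size is unknown, because the missing rate, the number of ongoing conditions and the record structure are not given. Under the assumptions above it is small for most terms and material only for conditions very common at baseline. Primary and secondary efficacy, the SAE comparison and the adjudicated safety outcomes are untouched. The correction is worth making because a stated rule gives a wrong answer and is cheap to put right.

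**What to change.** Add to SAP section 4.17.2: an event ongoing across the first post-randomization injection, with no recorded post-baseline severity and no reported change, carries its baseline severity (recorded or assumed) into the post-baseline period and is not treatment-emergent. The severe assumption applies to events with onset on or after that injection, and to ongoing events with a reported worsening but no grade.

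With the same grade on both sides, the first three rows of the Step 1 table become 1 vs 1, 1 vs 1 and 2 vs 2, and none is a TEAE. Reported worsenings without a grade keep the cautious default.

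The cost is one addition to the SAP and a small programming change. The downside is that a real worsening which the site neither graded nor reported as a change would not be counted.

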4.17.2.1. Serious Adverse Events

A SAE is any AE from this study that results in one of the following outcomes (please note exceptions outlined below):

- death (except as noted below)

- initial or prolonged inpatient hospitalization
- a life-threatening experience (that is, immediate risk of dying)
- persistent or significant disability/incapacity
- congenital anomaly/birth defect
- considered significant by the investigator for any other reason.

The following primary, secondary, and additional efficacy events will not be required to be reported as AEs or SAEs *unless* the investigator believes the event may have been caused by the study drug, drug delivery system, or study procedure:

- death
- nonfatal MI
- nonfatal stroke
- hospitalization for HF or an urgent HF visit
- hospitalization for unstable angina
- coronary, carotid, or peripheral revascularizations

If one of the above endpoint events is reported but does not meet a prespecified event definition detailed in the CEC Charter, as reviewed by the independent CEC, the study site subsequently will be required to report the event as an AE or SAE to comply with regulatory reporting requirements.

All SAEs will be compared between treatment groups at the PT level in the ITT population.

4.17.2.2. Treatment-Emergent Adverse Events Leading to Permanent Discontinuation of Study Drug or Study Withdrawal

Patients may permanently discontinue study medication but are expected to remain in the study. Separate analyses will be performed to compare the treatment groups with respect to AEs that led to permanent discontinuation of study medication and AEs that led to withdrawal from the study. These analyses will be conducted for all randomized patients.

4.17.3. Laboratory Analytes

All laboratory measurements will be performed locally except calcitonin which will be performed by a central laboratory. For analyses, the laboratory measurements will be converted to SI units. The following laboratory measurements will be analyzed: calcitonin, creatinine, eGFR, serum creatinine, urine ACR, HbA1c (Section 4.15.1) and lipids (Section 4.17.3.1).

Laboratory measurements collected at scheduled and unscheduled visits will be listed by patient by visit using all randomized patients. An additional listing will be presented for all scheduled and unscheduled laboratory measurements that are outside the SI normal range. All summary

analyses will be based on the ITT population. Laboratory measurements that fall within a visit window (± 30 days around the observed visit date) will be associated with that visit. Scheduled visits will have a ± 15 -day window around the scheduled visit date. For multiple runs of the same laboratory analyte, the laboratory measurement within the window that was taken closest to the visit date will be representative of that patient's lab value for that visit.

The eGFR values will be calculated using the MDRD equation [eGFR (mL/min/1.73 m²) = 175 X standardized Scr^{-1.154}Xage^{-0.203} X1.212 [if black] X 0.742 [if female], (Levey et al. 2006)].

Section 4.2 describes the analysis for continuous laboratory measurements. Microalbuminuria is defined as a urine ACR >30 mg/g and ≤ 300 mg/g) and macroalbuminuria (clinical proteinuria) as urine ACR >300 mg/g). Urine ACR is calculated as the ratio of urine albumin and creatinine measured from a morning urine sample or a random urine sample if a morning sample is not available.

The proportion of patients with microalbuminuria or macroalbuminuria at baseline or during the study will be compared between treatment groups at by visit. Shift tables will be presented for urine ACR. The tables will show the proportions of patients with shifts in the laboratory results from baseline to maximum post-baseline result using categories based on the Central Laboratory reference ranges. The categories for urine ACR will be ≤ 30 mg/g, >30 mg/g to ≤ 300 mg/g and >300 mg/g. Shifts will be grouped to show the proportions of patients who experienced decreases (post-baseline category $<$ baseline category), increases (post-baseline category $>$ baseline category), or no change from baseline to maximum post-baseline result for each treatment. Baseline will be the last non-missing observation in the study period from screening to randomization (Visit 1 through Visit 3). The maximum post-baseline result in the postbaseline study period (Visits 3 and beyond) will be the maximum result for the analysis. The analyses will use both scheduled and unscheduled labs and will be in all randomized patients with at least 1 baseline and 1 post-baseline urine ACR measurement.

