## 8.2. Exclusion Criteria

Patients will be excluded from the study if they meet **any** of the following criteria:

- [10] Uncontrolled diabetes requiring immediate therapy (such as diabetic ketoacidosis) at screening or randomization, in the judgment of the physician.
- [11] Have experienced a severe hypoglycemic episode within 1 year prior to randomization.
- [12] Have experienced an acute coronary or cerebrovascular event within 2 months prior to randomization.
- [13] Are currently planning a coronary, carotid, or peripheral artery revascularization.
- [14] Have known chronic renal failure (defined as a known eGFR <15 mL/minute/1.73m^2) or are on chronic dialysis at screening.
- [15] Have a known clinically significant gastric emptying abnormality (for example, severe diabetic gastroparesis or gastric outlet obstruction) or have undergone gastric bypass (such as bariatric) surgery.
- [16] Have a past history of chronic, acute, or idiopathic pancreatitis or signs/symptoms of pancreatitis.
- [17] Have severe hepatic dysfunction such as portal hypertension or cirrhosis, acute or chronic hepatitis, signs or symptoms of any other liver disease, or an alanine transaminase (ALT) level  $\geq$ 3.0 times the upper limit of normal (ULN) for the reference range at screening.

- [18] Have a) any self or family history of medullary C-cell hyperplasia, focal hyperplasia, carcinoma (including sporadic, familial or part of multiple endocrine neoplasia MEN 2A or 2B syndrome), or
- b) any known self or family history of type 2A or type 2B multiple endocrine neoplasia (MEN 2A or 2B) in the absence of known C-cell hyperplasia. This includes patients with a family history of MEN 2A or 2B whose family history for the syndrome is RET negative. The only exception for this exclusion will be patients whose family members with MEN 2A or 2B have a known RET mutation and the potential patient for the study is negative for that RET mutation.
- [19] Have a calcitonin value  $\geq 20$  pg/mL according to the central laboratory measurement at screening.
- [20] Are previous organ transplant recipients or are awaiting an organ transplant (corneal transplants [keratoplasty] are allowed).
- [21] Are taking a weight loss drug (over-the-counter or prescription) and are unwilling or unable to discontinue the drug at the time of screening or are taking pramlintide at the time of screening.

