#### **10.2.2.3.2. Medullary Thyroid Carcinoma and C-Cell Hyperplasia**

Medullary thyroid carcinoma (MTC) presents as part of an autosomal dominant inherited disorder in about 20% to 25% of cases and as a sporadic tumor in the balance of the cases. From the familial cases a progression from C-cell hyperplasia to microcarcinoma and eventually macroscopic carcinoma has been delineated by following calcitonin (Wolfe et al. 1973). Since calcitonin is being monitored, events of MTC and C-cell hyperplasia may be detected at very early stages before these lesions become clinically symptomatic. Physiologic or secondary C-cell hyperplasia with mild elevations of calcitonin may be associated with follicular diseases such as Hashimoto's thyroiditis and follicular neoplasms and with aging, hyperparathyroidism, and hypergastrinemia (Perry et al. 1996; LiVolsi 1997).

If a patient is diagnosed with MTC, the patient must permanently discontinue study drug.

Calcitonin, a 32 amino acid peptide, is excreted primarily by the kidneys and may be elevated in moderate to severe renal dysfunction. Approximately 30% of individuals with renal insufficiency (stage not specified) will have some degree of hypercalcitoninemia due to secondary hormonal stimulation and poor clearance. At any level of renal insufficiency, a nonstimulated calcitonin of  $\geq 40$  pg/mL would provide nearly 100% sensitivity for MTC with specificity of approximately 60%.

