##### **10.2.2.3.3.1. Calcitonin Monitoring**

Participants in this trial will have measurements of calcitonin taken according to the Study Schedule ([Attachment 1](#)). The purpose of calcitonin monitoring is to assess the potential of dulaglutide to affect the thyroid C-cell function, which may indicate development of C-cell hyperplasia and neoplasms.

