##### **10.2.2.3.3.2. Calcitonin Monitoring Algorithm**

After randomization, if a patient is observed to have a serum calcitonin  $>35$  pg/mL, a calcitonin measurement must be repeated within 1 month. If the repeat value is  $<35$  pg/mL, the patient may continue in the trial on study drug and will continue to be followed per the Study Schedule ([Attachment 1](#)). If the repeat value is confirmed  $>35$  pg/mL, the patient must permanently discontinue study drug. The patient should undergo additional endocrine assessment and longer term follow-up by a thyroidologist or endocrinologist.

Data on patients who are requested to undergo further thyroid assessment either due to the calcitonin algorithm, development of thyroid neoplasms or for any other clinical reason will be

prospectively collected during the study. The independent CEC will adjudicate thyroid evaluations that result in a surgical biopsy of the thyroid gland and/or a thyroidectomy or a diagnosis of a thyroid malignancy or C-cell hyperplasia. The CEC Charter will contain the final detailed event definitions used for adjudication. Study sites should send the requested source documentation to the CEC in a timely fashion for adjudication of the event.

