For continuous lab measurements, an analysis of variance (ANOVA) on rank-transformed data will be used and p-values for the difference between dulaglutide and placebo will be reported, unless stated otherwise. The model includes treatment. Treatment group comparisons will be performed with no multiplicity adjustment. Categorical laboratory measures will be analyzed using Chi-square test or Fisher's exact test.

In situations where the continuous response variable will be expected to violate the assumption of normality, Wilcoxon's rank sum test will be used. Such situations will be appropriately identified throughout this SAP. Between-treatment comparisons will be assessed using the p-value, and within-treatment changes will be assessed using the p-value from the signed rank test. Summaries for these variables will include descriptive statistics: number of patients, median, and 25th and 75th percentiles. In addition, the Hodges-Lehman estimator of the treatment contrast will be provided.

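### The SAP tests calcitonin only by ranks and plans no between-arm comparison of patients reaching the protocol's own 20 and 35 pg/mL cut-offs

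*SAP*

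**What the plan says.** Protocol 10.2.2.3.3.1 gives the aim: "The purpose of calcitonin monitoring is to assess the potential of dulaglutide to affect the thyroid C-cell function". Two cut-offs follow. Exclusion criterion [19] in Protocol 8.2 removes candidates at or above 20 pg/mL "according to the central laboratory measurement at screening", and Protocol 8.2.1 explains that such patients are more likely to have C-cell abnormalities. After randomization, Protocol 10.2.2.3.3.2 says that for a patient "observed to have a serum calcitonin $>35$ pg/mL, a calcitonin measurement must be repeated within 1 month". If the repeat is also above 35 pg/mL, study drug stops permanently (also Protocol 8.3.3).

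The analysis plan is generic. SAP 4.17.3 states "The following laboratory measurements will be analyzed: calcitonin, creatinine, eGFR, serum creatinine, urine ACR, HbA1c", together with lipids, and refers to Section 4.2 for the method. The method is actually in SAP 4.3.2: for continuous laboratory values, "an analysis of variance (ANOVA) on rank-transformed data will be used and p-values for the difference between dulaglutide and placebo will be reported", with treatment as the only term. Protocol 12.2.9.4 gives the same method. SAP 4.3.2 adds "Categorical laboratory measures will be analyzed using Chi-square test or Fisher's exact test", but no calcitonin category is defined anywhere. Urine ACR does get categories, proportions by visit and a baseline-to-maximum table: "Shift tables will be presented for urine ACR".

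**The concern.** A rank test asks whether one arm's values tend to sit higher overall. If the drug affected C-cells in only a small share of patients, the difference would lie in the top one percent or so of values, where ranks carry little information. The cut-offs that the protocol itself uses point at that part of the distribution. A plan without a count at those cut-offs could report no calcitonin difference while noticeably more patients in one arm reached them.

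Renal function adds a question of interpretation. Protocol 10.2.2.3.2 notes that calcitonin "may be elevated in moderate to severe renal dysfunction", and eligibility in Protocol 8.1 admits patients with persistent eGFR below 60 mL/min/1.73 m². No calcitonin analysis refers to eGFR.

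**Working it through.** **Inputs from the documents.** About 9600 patients (Protocol 12.1) randomized 1:1 (SAP 4.4), so n = 4800 per arm. Two-sided alpha is 0.05 (SAP 4.2). The documents give no rate, effect size or power for calcitonin, so there is no calcitonin figure to reproduce. As a check on the general inputs, the Schoenfeld formula gives the initial event target: 4 × (1.960 + 1.282)² / (ln 0.82)² = 1068 after rounding, against 1067 in SAP 4.1.

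**Assumptions.** The share p of placebo patients over the cut-off is set between 0.1% and 2% and doubled on dulaglutide. Each patient contributes one value to both tests. In simulation, 0%, 50% or 80% of values are tied at the assay's lower limit.

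**Threshold comparison.** Power = Φ(p / SE − 1.96), with SE = √{[p(1−p) + 2p(1−2p)] / n}. For 0.5% vs 1%: SE = √(0.014875 / 4800) = 0.00176, 0.005 / 0.00176 = 2.84, power = Φ(0.88) = 81%.

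**Rank test, small subset affected.** About a share p of dulaglutide patients move from the body of the distribution to its top. Each raises their chance of exceeding a placebo patient from about one half to about one, so P(Y > X) rises by about p/2. The standard error is √[(1/12)(2/4800)] = 0.00589. For p = 0.5%: z = 0.0025 / 0.00589 = 0.424, power = Φ(0.424 − 1.96) + Φ(−0.424 − 1.96) = 7.1%.

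| Placebo vs dulaglutide | Expected patients | Rank test, formula | Rank test, simulated (0 / 50 / 80% tied) | Threshold test, formula |
|---|---|---|---|---|
| 0.1% vs 0.2% | 4.8 vs 9.6 | 5.1% | 5.0 / 5.2 / 5.0% | 24% |
| 0.25% vs 0.5% | 12 vs 24 | 5.5% | 6.0 / 4.6 / 6.8% | 52% |
| 0.5% vs 1% | 24 vs 48 | 7.1% | 7.8 / 7.8 / 10.8% | 81% |
| 1% vs 2% | 48 vs 96 | 13.6% | 10.0 / 13.6 / 19.8% | 98% |
| 2% vs 4% | 96 vs 192 | 39.6% | 42.6 / 45.8 / 68.2% | >99% |

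Each simulated cell used 500 runs.

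**Rank test, whole distribution shifted.** Going from 0.5% to 1% over a cut-off on a normal (log) scale needs a shift of 2.576 − 2.326 = 0.25 SD. Then P(Y > X) = Φ(0.25 / √2) = 0.570, and z = 0.070 / 0.00589 = 11.9. In simulation (200 runs per cell) rank-test power was 100% at every rate and tie fraction, above the threshold test at the low rates.

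**Other routes by which a crossing could reach a table**
- Discontinuation of study drug is compared by arm and by reason (SAP 4.12, 4.17.1.2). The example reasons are adverse event, protocol and patient decision; calcitonin is not named. Patients between 20 and 35 pg/mL, or already off drug, do not enter by this rule.
- Treatment-emergent events are compared by preferred term, and events leading to permanent discontinuation by arm (SAP 4.17.2, 4.17.2.2). This depends on the site reporting the value as an event.
- MTC, other thyroid carcinoma and C-cell hyperplasia are compared on adjudicated events (SAP 4.17.1.2). Adjudication needs a surgical biopsy, a thyroidectomy or a diagnosis (Protocol 10.2.2.3.3.2).
- Out-of-range values are listed (SAP 4.17.3), with no comparison.

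None of these is a between-arm comparison at 20 or 35 pg/mL.

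**The case against.** The strongest reply is that the mechanism decides the matter. The stated purpose concerns C-cell function, and a drug that moved calcitonin generally would be caught by the rank test with near certainty. A reader might infer that a doubling of patients over the cut-offs would go undetected. The documents do not support that: it is true only if the effect is confined to a small subset, and nothing in them says that a C-cell effect must take that form.

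Second, confirmed values above 35 pg/mL are not invisible. They force discontinuation, lead to endocrine assessment, and may appear as adverse events or adjudicated diagnoses. This stands: the signal would be scattered over several tables, not necessarily lost.

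Third, 20 pg/mL is a screening criterion with no role after randomization, and crossings of the 35 pg/mL action limit must be rarer still. If those fall at 0.25% or below on placebo, the threshold test also has about 50% power or less. This stands too, although counts with confidence intervals are informative whatever the power.

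Fourth, SAP 4.17.3 refers to categories from central-laboratory reference ranges for its shift tables, and calcitonin is the only centrally measured analyte. That wording is unclear, but the paragraph names urine ACR and gives categories for ACR alone.

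Finally, a reader might want the comparison split by eGFR at the time of the calcitonin sample, to separate a renal from a C-cell effect. That conditions on a post-randomization variable the drug may change (eGFR decline is part of a secondary endpoint), so it would not separate them cleanly.

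**Conclusion.** The gap is real and limited. The SAP applies one rank-based test to calcitonin and plans no between-arm comparison at the cut-offs on which the protocol acts. Under a small-subset effect with 4800 per arm, the rank test has about 7-11% power for a doubling from 0.5% to 1% and 10-20% for 1% to 2%, against about 81% and 98% for a threshold comparison. These figures rest on assumed placebo rates and tie fractions. They apply to whichever cut-off has those rates, which may not be true of 35 pg/mL.

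Two further inferences go too far. A reader might conclude that the plan is blind to calcitonin: it is not, since a general shift would be found and other tables give a partial view of values above 35 pg/mL. A reader might also take C-cell assessment as a reason for the trial's length. Protocol 7.3 ties duration to the count of cardiovascular events and presents thyroid assessment as something the length also allows.

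**What to change.** Add to SAP 4.17.3, by arm:

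- the number and proportion of patients with any post-baseline calcitonin ≥20 pg/mL, any >35 pg/mL, and >35 pg/mL confirmed on repeat, each with risk difference and 95% CI;
- time to first crossing by the Cox model, or Fisher's exact test if there are fewer than 10 events, as in SAP 4.3.4;
- a shift table from baseline (Visit 1, as in Protocol 12.2.9.4) to the maximum post-baseline value.

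Use all scheduled and unscheduled central-laboratory values. The visit-window rule in SAP 4.17.3 keeps only the value closest to the visit, so a repeat taken within a month could displace the first result or be dropped.

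Keep the rank analysis alongside, and correct the reference from Section 4.2 to 4.3.2. If renal function is considered, use baseline eGFR subgroups, descriptively. Do not use concurrent eGFR for inference.

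The cost is a few extra tables without multiplicity control, to be labelled as such. Calcitonin is already measured about yearly in the central laboratory, so no new samples are needed and no clinical rule changes.
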